We plan to recruit 24 English-speaking participants aged 50 years and older with aMCI and a history of TBI, all of whom have problems with episodic memory. Participants can be referred from identified providers at UT Southwestern Medical Center, Parkland Health & Hospital System, Veteran's Affairs Hospitals, or other locations in the DFW area with providers that are aware of this research effort. All recruitment procedures will take place at UTSW locations, as well as all research visits. All participants will have at least 12 years of education and a history of TBI as determined by VA/DOD criteria. Participants will be randomized into an active HD-tDCS condition or a sham condition with a 2:1 ratio of active (n=16) to sham (n=8) participants in order to assess the efficacy of HD-tDCS on improving episodic memory. The proposed study will measure response to treatment with 1 mA anodal HD-tDCS over the preSMA/dACC region when compared to sham. Participants will receive 10 sessions of active stimulation (1 mA anodal HD-tDCS targeting preSMA/dACC for 20 min) or sham across 2 weeks. Episodic memory tasks will be completed at baseline, immediate follow-up after session 10, and a 3-month follow-up.

Visits

Below is a table summarizing the study visits followed by a detailed description of the procedures for each visit. It is a 12 day study with a follow-up session twelve weeks after the last day.

TABLE 1. SUMMARY OF VISITS

| Visit | PROCEDURES | TIME |
|-------------|---|-------------------|
| Visit 1 | Pre-testing neuropsychological assessment | 1 hour |
| Visits 2-10 | HD-tDCS active or sham stimulation | 30 minutes |
| Visit 11 | HD-tDCS active or sham stimulation and post-testing neuropsychological assessment | 1 hour 30 minutes |
| Visit 12 | 12-week follow-up assessments | 1 hour |

Visit 1: Pre-testing neuropsychological assessment (approximately 1 hour)

Assessments: At UTSW's Cognitive and Memory Disorders Clinic, participants will first be asked to complete the Ohio State University TBI Interview Method (OSTBIIM) to characterize TBI history and severity. Afterwards, a neuropsychological evaluation will be completed consisting of the following measures:

1. Hopkins Verbal Learning Test-Revised (HVLT-R)
2. Brief Visuospatial Memory Test-Revised (BVMT-R)
3. Controlled Oral Word Association Test
4. Wechsler Adult Intelligence Scale-IV Digit Span
5. Trail Making Test
6. Stroop Color and Word Test
7. Beck Depression Inventory-2

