For the active condition, administration parameters will consist of the stimulation being ramped up over 60 seconds until it reaches 1 mA, maintained for 20 minutes, and then ramped down over 60 seconds at each session. The anode will be placed over Fz according to the International 10-20 EEG system, corresponding to the approximate location of the preSMA/dACC. Four return cathodal electrodes will be placed approximately 5 cm radially from Cz; corresponding to locations Fz, FPz, F7, F8 and Cz. 20 minutes of 1 milliamp of anodal HD-tDCS per session.

For the sham condition, parameters will consist of current being ramped up over 60 seconds until it reaches 1 mA and then stopped. (This allows for the same scalp sensation for both the sham and active condition so that subject and experimenter will remain blinded). This ramp up for one minute and then stopped and off for 19 minutes will be given each 20-minute sham session to keep the timing and subjective experience similar to the active condition.

Visit 11: HD-tDCS active or sham stimulation + Post-assessment (1 hour and 30 minutes)

HD-tDCS Stimulation: Participants will receive a final session of either active stimulation (1 mA anodal HD-tDCS targeting preSMA/dACC for 20 min) or sham. The stimulation current will gradually ramp up to 1mA during the first 60 seconds of stimulation, and remain for 19 minutes in the active stimulation group, but turned off afterwards for the sham group. Participants will also undergo the same neuropsychological assessments as in Visit 1.

Visit 12: 12-week Follow-up Neuropsychological Assessments

After 3 months from their last session, post-neuropsychological assessment will be completed to see if previously acquired gains remain over this time frame. Neuropsychological measures will be the same as in Visit 1.

Summary of Study Team's Experience Using HD-tDCS:

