This study may contribute to developing a new non-pharmacological method for the treatment of episodic memory difficulties in individuals with aMCI following traumatic brain injury. Given only a slight risk to participants and the greater possibility of long-term benefits to the knowledge base, the risks/benefits ratio seems reasonable.

14. Biostatistics:

Linear mixed modeling (LMM) will be used to assess performance growth as a function of group (i.e., number of sessions) and assessment period. Primary outcomes will be measures of episodic memory from the neuropsychological battery. Additionally, baseline assessments on neuropsychological measures, TBI severity, use of cholinesterase inhibitors, and demographics variables will allow for assessing individual differences prior to the intervention as a predictor of response to the proposed treatment schedules. LMM will allow for testing change scores from baseline as a function of group and assessment session. Obtaining combined linear and quadratic fit parameters will allow for estimating points of asymptote in the gain functions per outcome to identify optimal delivery protocol parameters. We will use restricted maximum likelihood estimators (ReML) of the variance components to compute the maximum likelihood estimators of the fixed effects parameters (i.e., group, session, and group*session interaction effects). Thus, we will not exclude participants with missing time points. All available data on all participants who 1) meet inclusion/exclusion criteria, 2) have been randomly assigned to groups, and 3) provide baseline data will be used regardless of whether they complete the trial. (Depending on the amount of dropout, analyses also will be carried out to identify any biases in dropouts per group.)

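### Section 14 does not commit the mixed model to adjusting the active-minus-sham contrast for the baseline score; the unadjusted change contrast is valid but usually less precise

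*Combined protocol and SAP*

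**What the plan says.** Section 14 (Biostatistics) describes a linear mixed model fitted by REML. It gives the "fixed effects parameters (i.e., group, session, and group*session interaction effects", and adds that "LMM will allow for testing change scores from baseline as a function of group and assessment session". Baseline scores have a separate role: together with TBI severity, cholinesterase inhibitor use and demographics, they "will allow for assessing individual differences prior to the intervention as a predictor of response". On the endpoint it says only that "Primary outcomes will be measures of episodic memory from the neuropsychological battery". Participants who meet the entry criteria, are randomised and "provide baseline data will be used regardless of whether they complete the trial".

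Section 4 (Study Procedures) shows that the baseline value of every outcome will be on hand. For Visit 11, "Participants will also undergo the same neuropsychological assessments as in Visit 1"; for Visit 12, "Neuropsychological measures will be the same as in Visit 1". The overview in Section 4 sets a "2:1 ratio of active (n=16) to sham (n=8) participants".

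Neither section says that the treatment contrast is adjusted for the baseline score, or that the two arms share one baseline mean. No correlation, SD, effect size, alpha or power is given.

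**The concern.** Randomisation makes the two arms equal at baseline in expectation. A model with free group, session and group-by-session effects does not use this. It estimates a separate baseline mean in each arm and subtracts the whole observed baseline difference from the follow-up difference. Unless baseline and follow-up are very highly correlated, this over-corrects and adds noise.

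With only 8 sham participants, precision is scarce. If a moderate correlation holds, the listed contrast gives away the information of several participants, and data already collected would recover it. Leaving the matter open also lets the choice between an adjusted and an unadjusted contrast be made after results are seen.

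**Working it through.** **No figure to reproduce.** The allocation is consistent (24 × 2/3 = 16, 24 × 1/3 = 8). The total of 24 comes without a power calculation.

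**What the listed model estimates.** With complete data and session as a category, each group-by-session coefficient relative to baseline equals the difference in mean change from baseline. A REML fit to one simulated data set (16 against 8, three visits) confirmed this: coefficients 0.1990 and 0.1614, differences in mean change 0.1990 and 0.1614. Modelling change scores at the two follow-ups gives the same contrast at each visit. With missing visits the equality is approximate.

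**Inputs.** 16 and 8 come from Section 4. Assumptions: complete data, one follow-up visit, baseline SD 1, follow-up SD s, and correlation ρ between them.

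**Formulas.** Let D = 1/16 + 1/8 = 0.1875.

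- Unadjusted change contrast: variance = (1 + s² − 2ρs) × D, which is 2(1 − ρ) × D when s = 1.
- Baseline-adjusted contrast: variance = s²(1 − ρ²) × D × [1 + 1/(24 − 4)]. The factor 1.05 is the expected price of estimating one baseline slope.
- Ratio at s = 1: 1.05 × (1 + ρ)/2.

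**Equal SDs (s = 1).** The last column is 24 × (1 − ratio).

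| ρ | Unadjusted | Adjusted | Ratio | Participants |
|---|---|---|---|---|
| 0.5 | 0.1875 | 0.1477 | 0.788 | 5.1 |
| 0.7 | 0.1125 | 0.1004 | 0.893 | 2.6 |
| 0.8 | 0.0750 | 0.0709 | 0.945 | 1.3 |
| 0.9 | 0.0375 | 0.0374 | 0.998 | 0.1 |

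Simulation with 40,000 trials per ρ gave ratios of 0.791, 0.892, 0.947 and 1.003. Break-even is ρ = 2/1.05 − 1 = 0.905, or 0.894 on confidence interval width (21 against 22 degrees of freedom).

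**Unequal SDs.**

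| s | ρ = 0.5 | ρ = 0.7 | ρ = 0.8 | Change more precise for ρ |
|---|---|---|---|---|
| 1.1 | 0.858 | 0.967 | 1.016 | about 0.77 to 0.97 |
| 1.2 | 0.915 | 1.015 | 1.047 | about 0.67 to 0.92 |

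For example, at s = 1.1 and ρ = 0.8: 1.05 × 1.21 × 0.36 / (1 + 1.21 − 1.76) = 0.4574/0.45 = 1.016. If s is 0.95 or less, adjustment is more precise at every ρ.

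**Upper limit on the loss.** Since 1 + s² − 2ρs = s²(1 − ρ²) + (1 − sρ)², the ratio cannot exceed 1.05, whatever s and ρ are.

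**Power, equal SDs, two-sided 0.05.** Listed model against a constrained-baseline model, both with unstructured covariance, one common ρ among the three visits and small-sample degrees of freedom (20,000 simulated trials per cell):

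| True benefit | ρ = 0.5 | ρ = 0.7 | ρ = 0.8 | ρ = 0.9 |
|---|---|---|---|---|
| 1 SD | 59% vs 70% | 81% vs 86% | 94% vs 95% | no gain |
| 0.5 SD | 20% vs 25% | 30% vs 33% | 42% vs 45% | 69% vs 70% |

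The least favourable comparison sets the listed model with compound symmetry against a single-visit analysis of covariance. For a 1 SD benefit the gain is then about 8, 2 and 0 points at ρ = 0.5, 0.7 and 0.8.

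**Type I error (same simulation).** The constrained-baseline model with Kenward-Roger rejects 5.0 to 5.3% under the null. With Wald z it rejects 7.4 to 7.8%, against 6.3 to 6.5% for the listed unstructured model. Dropout was not simulated.

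**The case against.** Four points can be made for the plan as written.

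1. **The list of effects may not be meant as closed.** It stands in a sentence about REML estimation, and the same paragraph names baseline scores as predictors of response. A baseline main effect in a change-score model would be the adjustment asked for here. This stands as far as it goes: a reader might infer that the plan rules out adjustment, and the text does not support that. It leaves the matter open, so the point is a missing commitment.

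2. **The benefit rests on inputs that the documents do not give.** This stands. A reader might infer that adjustment wins whenever the correlation is below 0.9, but that needs equal SDs. A wider spread at follow-up is plausible if response varies among people enrolled for poor memory, and it lowers the threshold. Against that, the possible loss is capped at about 5% of variance, while the gain at a correlation of 0.5 with equal SDs is about 21%.

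3. **More basic items are open.** Section 14 names no single memory score, visit or test, and glosses group as a count of sessions although the design compares active with sham. These do need settling. They do not remove this point, and the efficacy contrast should be named in the same edit.

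4. **The recommended model depends more on small-sample inference.** This is correct, as the Wald z figures show, and the fix has to include it.

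**Conclusion.** The point holds as one of efficiency. Section 14 does not commit to a baseline-adjusted treatment contrast, and its listed effects give an unadjusted difference in change. Under 16 against 8, complete data, one follow-up visit and equal SDs, the avoidable variance is about 21% at a correlation of 0.5, 11% at 0.7, 5.5% at 0.8 and none at 0.9. With a larger SD at follow-up the gain shrinks and can turn into a small loss.

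Two stronger conclusions do not follow. A reader might infer that the planned estimate is biased or the test invalid; under randomisation the change contrast is unbiased, and no stated figure is wrong. A reader might also infer that adjustment would give the pilot adequate power; for a 0.5 SD benefit the gain is only 1 to 5 points across the correlations tabulated, and power stays low at moderate correlations.

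The change is worth making because it is cheap and its downside is bounded. The study does not fail without it.

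**What to change.** In Section 14, pre-specify the efficacy model as a REML mixed model of the scores at all three visits, with visit as a category, a common baseline mean for both arms, group terms at the two follow-ups, an unstructured 3 × 3 covariance and Kenward-Roger degrees of freedom. Participants with baseline data only stay in, so the stated analysis set does not change.

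An alternative is to model the two follow-ups with the baseline score and its interaction with visit as covariates, also with Kenward-Roger. Participants with baseline data only then contribute nothing.

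Name in advance the active-minus-sham contrast, at one follow-up visit chosen by the investigators, as the efficacy test. If change scores are modelled instead, group-by-session should not be that test, because it is zero when the benefit is equal at both follow-ups.

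The covariance structure should be stated. When correlations fall over time (0.7, 0.5, 0.6 or 0.8, 0.6, 0.7 for baseline–immediate, baseline–3-month and immediate–3-month), compound symmetry gave type I error of 8.0 to 9.0% for the listed model and 7.3 to 8.3% for the constrained one at 3 months. Unstructured covariance with small-sample degrees of freedom kept 5.0 to 5.3%.

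The cost is a few sentences, no new data and one or two degrees of freedom. There is little or no gain if the correlation is high, and Wald z must not be used. Behaviour under dropout remains to be checked.
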